7.1.2. Exclusion Criteria

The following are criteria for exclusion from participating in the study:

1. Schirmer test (with anesthesia) ≤ 2 mm in either eye at Screening;
2. Patients who are currently using topical ocular medication or have used topical ocular medication within 2 weeks of the Screening visit. Patients who are being treated bilaterally with a marketed artificial tear for dry eye can be considered, provided they discontinue use at the Screening visit;
3. Any active anterior segment disease excluding blepharitis;
4. Any systemic disease that may affect ocular health e.g. Graves disease, and auto-immune diseases such as ankylosing spondylitis, multiple sclerosis and systemic lupus erythematosus;
5. History of epilepsy or migraines exacerbated by flashing, strobe-like lights;
6. Rigid or soft contact lens wearer, including orthokeratology;
7. History of eye surgery within 6 months prior to enrolment in the study;
8. Previous corneal refractive surgery;
9. Known allergy or sensitivity to the study product(s) or its components;
10. Females who are pregnant (self-report), nursing, or planning a pregnancy.

7.2. Participant Withdrawal

Participants may be permanently discontinued from the clinical trial for any of the following reasons:

- If, in the Investigator's opinion, it is in the best interest of the participant;
- Persistent clinical trial-related symptoms/complaints that are not correctable;
- Has an adverse event that is related to the study eye drops and/or which, in the Investigator's or Sponsor's opinion, requires withdrawal of the participant;
- Participant voluntarily withdraws consent from the clinical trial (i.e. Revocation of Consent);
- Participant is lost to follow-up, or relocates and cannot attend the clinic;
- If a participant is not compliant with the clinical trial requirements and instructions e.g. visit schedule;

- Repeated protocol violations/deviations.

7.3. Withdrawal and Follow-up Procedure

Participants who are permanently withdrawn from the study should be seen as soon as possible after stopping use of the study eye drops for a final visit to assess participant safety and to return any unused study eye drops. This may be done at a routine clinic visit or an unscheduled visit if it occurs between routinely scheduled visits.

7.3.1. The Final Study Exit Visit

Where possible, the data requirements for the final study exit visit are the same assessments as for the 4 week assessment (Visit 4c) shown in Table 5. However, the minimum data requirements include:

- Visual acuity
- Slit-lamp biomicroscopy (ocular redness, corneal and conjunctival staining)

For withdrawal of consent, a 'Revocation of Consent' document should also be signed, if possible.

7.3.2. Lost to Follow-up

A participant will be considered lost to follow-up, after three documented and failed attempts have been made to contact the participant – two phone calls and one written. Any contact should attempt to gain the following information:

- reason participant has not returned to clinic
- safety (previous/new adverse events status), and
- concomitant therapies.

7.3.3. Event Follow-up

If a participant has experienced an adverse event that is continuing at the end of the study participation, the event is marked as ongoing. The Investigator should ensure appropriate follow-up care is arranged/provided to the participant as appropriate.

If an adverse event has occurred and is continuing, the participant should be followed until the event has resolved, or stabilised if there is no chance of improvement. Source notes and the reporting form should be updated as

appropriate, and the information forwarded to the Sponsor/HREC/TGA as necessary.

7.3.4. Whether and How Participants are to be Replaced:

Participants who experience an adverse response during the course of the study, that requires early discontinuation from the study, will not be replaced. Participants who are not suitable at Screening will be replaced, until the enrolment target is reached.

7.4. Early Termination of Trial

The trial may be stopped early for any one or more of the following reasons:

- If the monitoring of the clinical trial reveals unacceptable levels of adverse events, even though some of the participants may not be affected;
- If the Investigator does not adhere to the protocol;
- If the Sponsor decides to stop the study for any reason, with appropriate notification.

In the event of early termination of the trial, the HREC will be notified.

8. NUMBERING

Participant numbering will occur sequentially commencing with '001'.

9. EQUIPMENT TO BE USED / STANDARD & NON-STANDARD PRACTICE PROCEDURES

9.1. Standard Equipment and Procedures:

- **Visual Acuity:** Measurement of the standard of vision achieved with spectacles using standard letter charts. Measurements are taken under monocular conditions.
- **Slit-Lamp Biomicroscopy:** A specialised microscope with its own light source is used to examine the anterior eye including the Meibomian glands.
- **Fluorescein Assessment:** The ocular surface is assessed by instilling a harmless fluorescent dye called 'fluorescein' directly to the inferior bulbar conjunctiva using a sterile strip impregnated with fluorescein and moistened with sterile saline. The eye is assessed with the slit-lamp biomicroscope using a cobalt blue filtered light and a Wratten 12 filter.
- **LipiView® Ocular Surface Interferometer (TearScience®):** Will be used to measure the absolute thickness of the tear film lipid layer. The participant's eye is positioned in front of an illumination source that is directed toward the tear film on the corneal surface. The camera records a 20-second video of the tear film interference and subsequently displays a value in interferometric colour units (ICU), where 1 ICU approximates 1nm of lipid layer thickness.
- **Questionnaires:** Questions assessing eye symptoms and product usage will be administered on paper forms.
- **Participant History File:** Created at commencement of study and maintained throughout the trial. Contains relevant references to participant's medical history (both prior to participation in the trial and ongoing throughout the trial); and contains details of any problems encountered during the trial (either through observation by the investigator or as volunteered by the participant).

9.2. **Non-Standard Equipment and Procedures:**

Non-standard procedures that will be performed include:

- **Tear Evaporation Rate:** The Vapometer is a closed chamber device which is used for measuring transepidermal water loss.
- 
- **Photography/Video:** A photograph of the eye will be taken at the first visit, and photographs and video recording of any interesting/unusual findings may also be made for documentation and/or follow-up purposes at other visits.

9.3. **Maintenance and Calibration of Equipment**

Equipment will be monitored regularly for maintenance and calibration as per relevant company and product manuals.

10. TREATMENT OF PARTICIPANTS

10.1. Administration of Study Eye Drops

The study eye drops will be dispensed to each randomized subject at Visits 2a, 3a and 4a. Run-in product will be dispensed at Visits 1, 2c and 3c. Each subject will be instructed by the investigator to instill 1 to 2 drops in each eye, as needed, but at least 2 times daily. The same vial can be used for both eyes, and should be used one time only. The vial should be discarded after each usage. If the subject is concurrently using approved Restasis or glaucoma therapy drops during the study and run-in period, they should be instructed to wait a minimum of 15 minutes between drop instillations. Subjects should be instructed not to instill any eye drops within 3 hours prior to their scheduled study visits.

10.2. Study Product Storage and Accountability

10.2.1. Storage Requirements

The study product must be stored in a secure area. Only assigned study personnel authorized by the investigator may have access to study product. Study product can be administered only to subjects entered into the clinical study, at no cost to the subject, in accordance with the conditions specified in this protocol.

Study product must be stored at room temperature.

10.2.2. Accountability

A Study Product Tracking spreadsheet is used for keeping track of who, where and when study product has been issued or dispensed to.

- **Receipt of Study Product:** Once invoice has been checked, the study eye drops will be entered into the Study Product Tracking spreadsheet.
- **Issue of Study Product to Clinical Trial Participants:** The Optometrist is responsible for documenting the dispensing of the study product on the participant case record form and in the Study Product Tracking spreadsheet.
- **Disposal of Unused Supplies:** Instruction will be obtained from the sponsor as to how to handle returned, unused study product.

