6.1.2. Randomisation and Masking

Prior to initiation of study treatment, each subject who provides informed consent will be assigned to a subject number that will serve as the subject identification number on all study documents. Subject numbers will be assigned in ascending order and should not be omitted or reused.

At the Screening visit (Visit 1), all eligible subjects will receive run-in product (REFRESH PLUS) for use during the 14-day run-in period. The clinical site will dispense the run-in product. At the time of randomization (Visit 2, Arm 1), eligible subjects will be randomly assigned to 1 of the 3 treatments. A randomization scheme will be prepared in advance.

Study product will be labeled with study product kit numbers. At Visit 2 (Arm 1), the specific study product kit number for each randomized subject will be dispensed by unmasked administrative study personnel and all study measurements will be conducted by the masked investigator. Unused study product will be returned at the 4 week follow-up visit and the run-in product will be dispensed to be used during the wash-out period. This procedure will be repeated until all arms of the study have been completed.

The emulsion OM3 Tear formulation and the two comparator unit dose eye drops will be provided in similar 0.4 mL unit-dose vials (comparator products will have commercial labeling).

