12.2. Methods

Discomfort will be assessed using questionnaires and the Participant History File at all scheduled visits.

History (including medical and general health) will be recorded on the Participant History File at all visits.

Ocular examination using slit-lamp biomicroscopy will be carried out at baseline and at every visit. Ocular redness (bulbar) and corneal and conjunctival staining will be assessed and recorded using the CCLRU (Appendix II) and CIBA grading scales (Appendix III).

An optometrist will be available for the duration of the study. Participants will be advised to contact the optometrist immediately of any unusual event e.g. unusual redness, pain, irritation, etc. At the clinic, the optometrist will briefly assess the eye on a slit-lamp under low illumination to ascertain the nature of the condition, if any. If an adverse event occurs, the appropriate procedures will be conducted, including referral for medical treatment, if necessary. Any adverse events will be followed until complete resolution to the reasonable satisfaction of the participant and the investigator.

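### Section 10.2.2 gives the dispensing record to the Optometrist, a clinical assessor, and so leaves the assessor masking of Section 6.1.2 unprotected

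*Combined protocol and SAP*

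**What the plan says.** The synopsis and Section 6 describe a double-masked trial in which each participant uses all three products in random order.

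Section 6.1.2 contains the one explicit safeguard for the assessor. It provides that "the specific study product kit number for each randomized subject will be dispensed by unmasked administrative study personnel" and that "all study measurements will be conducted by the masked investigator". It adds that "Study product will be labeled with study product kit numbers", but also that "comparator products will have commercial labeling". On returns it says "Unused study product will be returned at the 4 week follow-up visit", without saying who takes them or at what point in the visit.

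Section 10.2.2 gives the record of dispensing to a different role: "The Optometrist is responsible for documenting the dispensing of the study product on the participant case record form". The same role makes the entry in the Study Product Tracking spreadsheet. The unmasked staff of 6.1.2 do not appear there.

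The optometrist has clinical duties elsewhere. Under 12.2, when a participant reports an unusual event, "the optometrist will briefly assess the eye on a slit-lamp under low illumination". Under 12.5, permanent discontinuation rests on the optometrist's opinion, or on the ophthalmologist's after referral. Case report forms are paper (14.1) and the Investigator signs them (15.1.4).

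**The concern.** Section 6.1.2 keeps those who know the allocation apart from those who assess. Section 10.2.2 blurs that separation by giving the allocation-related records to a clinical role that examines eyes and judges discontinuation, on a form that the Investigator later handles.

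Several outcomes depend on the observer. TBUT, a secondary endpoint, is timed by stopwatch to the first break-up that the observer accepts as genuine (11.2). Redness and staining are graded by eye on the CCLRU and CIBA scales. Adverse-event and discontinuation opinions are clinical judgements. An assessor who knew the product could shade any of these without intending to, and the analysis could not undo it. This is separate from whether the participant can recognise the product.

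**Working it through.** The plan gives no figure to reproduce. The check sets the duties side by side and then asks what must be true for masking to break by this route.

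| Task | Role named | Section |
|---|---|---|
| Dispense the kit | Unmasked administrative staff | 6.1.2 |
| Record the dispensing (form and spreadsheet) | Optometrist | 10.2.2 |
| Take all study measurements | Masked investigator | 6.1.2 |
| Examine the eye after an unusual event | Optometrist | 12.2 |
| Give the opinion on permanent discontinuation | Optometrist, or ophthalmologist after referral | 12.5 |
| Sign the case report form | Investigator | 15.1.4 |
| Receive unused product at 4 weeks | None named | 6.1.2 |

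Masking breaks by this route only if (a) an assessor sees the dispensing entry or the vials, and (b) what is seen identifies the product.

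**Condition (a).** For safety, the text puts the entry and the assessment with the same role, although more than one person could fill it. For efficacy it is plausible but not stated. No section in the reviewed text says that the Optometrist takes the efficacy measurements. If the Investigator who signs the forms is also the masked investigator, the measurer handles the form that holds the entry. If not, nothing bars the measurer from seeing it.

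**Condition (b).** The evidence points both ways. Kit numbering means that an entry need not name a product, and the spreadsheet is described as tracking to whom, where and when product was issued. Against that, a commercially labelled vial could identify a comparator on sight. The same spreadsheet logs receipt of supplies, and 15.1.4 requires quantities received to be reconciled with those used, discarded or returned. It could therefore carry product identity, but the documents do not say so. They name no holder of the key that links kits to products and no limit on who may open the spreadsheet.

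**Timing.** Section 6 places take-home dispensing after the Day 1 assessments, so exposure before those readings is not shown. The 4-week visit is different. Table 4 schedules tear evaporation, TBUT and biomicroscopy there, and 6.1.2 has product returned at that visit with no order fixed. Later periods are also open if earlier entries or vials have been seen. Each participant uses all three products, so identifying two of them reveals the third.

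**Count.** Up to 40 participants × 3 products = 120 dispensing records, and likewise up to 120 returns. These are opportunities for exposure, not unmaskings.

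**The case against.** The strongest defence is that dispensing, documenting and measuring are three different tasks. Both sections can be obeyed with masking intact if the Optometrist does not measure, or if only a kit number is written and the vials are not seen. That is right. A reader might infer that following both sections makes assessor masking fail; the documents do not support that. Pages removed before review may also define roles more closely.

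Four other tempting readings fail:

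- **The optometrist does the scheduled slit-lamp examinations.** The sentence in 12.2 concerns participants who report an unusual event. The scheduled examinations in 11.2 and 12.2 name no role.
- **The spreadsheet shows which product each participant received.** Product identity is not among its stated contents.
- **The assessor learns the allocation before the Day 1 readings.** Section 6 points the other way.
- **The assessor could choose which Vapometer readings to keep.** Section 11.2 fixes three measurements per eye under open-eye and closed-eye conditions and has each one recorded. It describes no discretion.

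It can also be said that the sentence on returns directly follows the one on unmasked staff, and that 10.2.1 limits product access to authorised staff. Neither names a recipient or excludes assessors.

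What remains is more than missing detail. Section 10.2.2 states a positive rule that puts dispensing records with a clinical assessor, when 6.1.2 already provides staff who could keep them.

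**Conclusion.** Sections 6.1.2 and 10.2.2 do not fit together in role, and assessor masking is left unprotected. Unmasking is possible but not established. It depends on two things that the available text leaves open: whether an assessor sees the entry or the vials, and whether what is seen identifies the product.

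The exposure is at most 120 records and 120 returns. The size of any bias cannot be derived from the documents. The risk is greatest for safety judgements, and for TBUT and the redness and staining grades at the 4-week visit. It is least for the Vapometer reading, which carries the primary endpoint. The change is a cheap improvement; the point does not show that the trial's masking has failed.

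**What to change.** Amend 10.2.2 so that the unmasked administrative staff of 6.1.2 document issue, return and disposal. Have them keep the tracking spreadsheet as a log closed to anyone who measures, grades or judges adverse events. Limit the case record form to the fact and date of dispensing. State that returned vials go to those staff before the 4-week examination begins.

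This works whether or not the Optometrist is the measurer. It takes a few sentences and moves one item off the form. No new staff are needed, and the downside is one separate log to reconcile. It does not remove the risk from commercially labelled comparators, which exists whoever keeps the record and needs its own answer.

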10.3. Concomitant Therapy

10.3.1. Permissible Medications/Treatments

Therapy considered necessary for the subject's welfare may be given at the discretion of the investigator. Systemic medications that **do not** cause or affect dry eye, dry mouth, changes in vision or other ocular changes are considered permissible medications. No topical ocular medication is allowed during the study, except for subjects meeting all inclusion and exclusion criteria for their use of monotherapy for glaucoma or OHT, or RESTASIS cyclosporine ophthalmic emulsion drops. Subjects using monotherapy for glaucoma or OHT, or RESTASIS, should continue to use their drops at the same dose and frequency for the duration of the study. If the permissibility of a specific medication/treatment is in question, please contact [REDACTED].

10.3.2. Prohibited Medications/Treatments

Contact lens use is prohibited during the study. Subjects are not allowed to have any scheduled or planned ocular or systemic surgery or procedure during the study that in the investigator's opinion may inhibit the subject's study participation.

Subjects are not allowed to receive temporary or permanent occlusion or cauterization of the lacrimal puncta during the study. After Screening, subjects should not begin or stop the use of any systemic medications that may affect a dry eye condition or affect vision (e.g. may cause blurred vision, cataracts, or glaucoma). Sites should look up the potential adverse reactions of each medication to ensure they do not fall within these exclusionary drug families. In addition, subjects should not **begin** using any topical ophthalmic medications such as topical cyclosporines, ophthalmic steroids, or glaucoma drops while enrolled in the study.

The decision to administer a prohibited medication/treatment is done with the safety of the study participant as the primary consideration. When possible, [REDACTED] should be notified before the prohibited medication/treatment is administered

10.4. Participant Instructions

General instructions to all participants

- Contact the clinic immediately if problems are experienced or if they have any questions or concerns
- Use the study eye drops provided only as instructed over the course of the study
- Instill 1 to 2 drops in each eye, as needed, but at least 2 times daily
- The same vial can be used for both eyes, and should be used one time only. The vial should be discarded after each usage.

11. ASSESSMENT OF EFFICACY

11.1. Parameters

- Subjective comfort
- History
- Visual acuity
- Eye photo
- Tear evaporation rate
- Lipid layer thickness
- Tear break-up time

- [REDACTED]
- [REDACTED]
- [REDACTED]
- [REDACTED]

11.2. Methods

Ocular comfort will be assessed by completion of paper-based questionnaires

[REDACTED]

History (including medical and general health) will be recorded on the Participant History File at all visits.

Habitual visual acuity will be measured at each visit using standard letter charts.

A photograph of the anterior eye will be taken at the Screening visit only for participants who are eligible to continue into the randomization phase of the study. From the photograph, ocular surface area will be measured in order to calculate the absolute tear evaporation rate.

Tear evaporation rate will be measured using the Vapometer. To minimize the effect of skin evaporation, petroleum jelly (Vaseline_, <http://www.unilever.com.au/brands-in-action/detail/Vaseline/299339/>) will be applied over the upper eyelid and the surrounding areas. Three measurements will be taken for each eye under open eye and closed eye conditions. Each measurement will be recorded and the absolute evaporation rate will be calculated for each eye.

Tear lipid layer thickness will be measured using the LipiView Ocular Surface Interferometer. The participant's eye is positioned in front of an illumination source that is directed toward the tear film on the corneal surface. The camera records a 20-second video of the tear film interference and subsequently displays a value in

interferometric colour units (ICU), where 1 ICU approximates 1nm of lipid layer thickness

Slit lamp biomicroscopy will be performed at each visit. This will be used to assess the following variables and rated using the CCLRU (Appendix II) and CIBA grading scales (Appendix III).

- Bulbar conjunctival redness
- Corneal and conjunctival staining (in conjunction with fluorescein and a Wratten 12 filter)

Tear break-up time (TBUT) will be performed with the application of fluorescein and a yellow barrier filter. A stopwatch will be used to record the first occurrence of true tear break-up, not just local thinning or tear film irregularity. Three consecutive TBUTs will be performed per eye and the time in seconds for each of the three measurements will be recorded.

